## **11.4 Measures to Minimize Bias**

### **Enrollment/ Randomization/ Masking Procedures**

After eligibility is assessed, informed consent is obtained and the woman has completed the ACASI survey and self-swab collection, she will be randomized to treatment arm. A blocked randomization scheme will be used to avoid “runs” in the randomization process. Each site will have its own blocked randomization scheme. Pre-numbered, sealed envelopes will be selected sequentially and opened for each participant who will then be enrolled in the indicated treatment arm. Because we are conducting a phase III trial and behaviors associated with the interventions are important, we will not attempt to make the single dose mimic a 7-day dose by supplementing with placebo. The trial will, therefore, be un-blinded. There will be no replacement of participants who discontinue early. Enrollment will continue through two months prior to study end.

Study personnel will know which arm the participant was randomized to. This information will not be disclosed to laboratory personnel. The Program Manager will periodically ensure that all participants were randomized to the correct treatment arm as indicated in the randomization scheme. Any discrepancies will be immediately discussed with investigators to prevent further error.

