## 11.7 Sample Size

### Considerations

[figure not shown]
This RCT will allow for evaluation of index dosing of MTZ by BV status. This study examines two hypotheses simultaneously:

H1: Women receiving multi-day MTZ will be less likely to test TV positive at TOC compared to women who receive the single dose MTZ.

H2: This effect (H1) will only be observed among women who have BV (Nugent score  $\geq 7$ ).

From our pilot work, we found the rates of repeat infection at TOC to be 16.2% for single dose and 10.7% for multi dose at a power of 0.80, we will need 1206 subjects. If we account for a 5% Inner Class Correlation (ICC) for correlation of the subjects within the 4 sites using the formula  $1=(M-1)*ICC$ . We will need to inflate by 15%. We will also inflate by 20% to accommodate for our anticipated follow-up for a required sample size of 1664. We will have 1332 evaluable unites at TOC, which will provide adequate power taking into consideration the ICC.

Figure 1.  
Randomization Scheme

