## 11.8 Maintenance of Trial Treatment Randomization Codes

Randomization will occur at the end of each baseline study visit. Randomization codes will be determined by a block randomization strategy at each site. Sealed envelopes will contain a study identification number on the outside and the randomization arm on the inside. Study staff will chose randomization envelopes sequentially and only open the card after enrollment, survey and specimen collection has occurred. There will be a separate staff member who will create and number the envelopes thereby shielding clinic study staff from knowing the randomization scheme. No study staff at the clinic will have access to the randomization database or numbering scheme. Every six months, a randomization interim analysis will be performed by Tulane staff for DSMB review to ensure that the randomization strategy is successful. The randomization arm will be noted on the study file and in the participant's data once the baseline visit is completed. No laboratory or clinical staff will have access to the randomization database.

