### **11.13 Final Analysis Plan**

Analyses will be conducted in an intent-to-treat manner with variables categorized per protocol. To assure that randomization has been achieved, selected demographic, clinical and behavioral (including medication adherence and sexual re-exposure) factors will be compared by study arms using chi-square, t-test or ANOVA, where applicable. If randomization was found to be successful (as indicated by even distribution of potential confounders) then analyses will be conducted with no need to adjust for confounding. If randomization was not achieved, then associations will be explored for potential confounding and if found these factors will also be included in the model. From the two aims, there are two hypotheses:

H1: Women receiving multi-day MTZ will be less likely to test TV positive at TOC compared to women who receive the single dose MTZ.

H2: This effect (H1) will only be observed among women who have BV (Nugent score  $\geq 7$ ).

Analysis: The research questions will be answered using a multivariable logistic regression analysis to examine the effect of single versus multi-dose (H1) and the differential impact of BV on this effect (H2). This primary logistic model contains two main effects (i.e. treatment and BV)

Version: 11.0

[figure not shown]
Version date: 1/2/17

and 1 first order interaction (BV by index treatment)). The model (1) will be:  $g(Y_i) = \beta_0 + \beta_1 + \beta_2 + \beta_1 \cdot \beta_2$  where:  $g(Y_i) = \log$  odds of repeat infection,  $\beta_0 =$  coefficient for the intercept,  $\beta_1 =$  (Factor 1) single versus multi-dose,  $\beta_2 =$  (Factor 2) BV at time of visit

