All analyses will be conducted in SAS by Tulane staff under the direction of [name]. Because we will use strict protocols and employ tight supervision of the study sites and the study populations are similar (mostly African American and underserved) we do not anticipate site variations but we will examine for any differences and if found, we will include a site variable in the models. We do not anticipate a three-way interaction, and our simulations (see below) support that belief. We will, however, run a fully parameterized model including all main effects, first order interactions, and second order interaction before running the primary analysis model (1) above. We will consider any p-value less than 0.05 to be significant and any p-value less than 0.10 as near-significant. If there is unexpected significant or near-significant interaction, we will stratify on BV status and assess the impact of index treatment (single vs. multi-dose) and any possible interaction separately for BV positive and BV negative women.

Additional analyses– The ACASI will allow for examination of index adherence to medication, index knowledge of partner treatment, sexual exposure and the nature of the sexual act and sexual partner, condom use. These factors will be assessed by arm to determine if any confounding occurred and if so, these analyses will be adjusted for these factors or stratified by these factors.

**Figure 4:** Algorithm for determining origin of repeat infection at TOC

**Outcome measures** – The study is powered for repeat infections. Since we will have information on sexual exposure and genotyping, we can also refine this outcome measure to examine treatment failure (H1 & H2) and reinfection and will use the algorithm depicted in figure 4.

All analyses will be conducted in SAS by the Tulane staff under the direction of [name]. As the data collection instruments are designed to

minimize missing data we do not anticipate an excessive amount. However, imputation techniques will be utilized to compensate for missing data (e.g. multiple imputation and maximum likelihood). Sensitivity analyses will be conducted to ensure that the method chosen to account for missing data does not bias the study’s results. Additionally, the characteristics of those who complete the study will be compared to those who drop out to determine whether drop out is informative. If not, multiple imputation methods will be used for initial analyses. If,

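### Site, the randomization stratum, enters the primary model only if unspecified differences are found; the effect is small, and making it a fixed term costs little

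*Combined protocol and SAP*

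**What the plan says.** Section 11.4 states: "Each site will have its own blocked randomization scheme". Section 11.8 agrees: "Randomization codes will be determined by a block randomization strategy at each site". Site is therefore the stratum of the randomization.

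Section 11.13 describes the primary model as follows: "This primary logistic model contains two main effects (i.e. treatment and BV", together with the interaction of the two. There is no site term. The same section expects no variation between sites, then adds: "we will examine for any differences and if found, we will include a site variable in the models". It does not state which quantity is compared, by which test, or in what form site would enter.

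Two other sentences in 11.13 might seem to settle this. One is the intention to "run a fully parameterized model including all main effects, first order interactions, and second order interaction before running the primary analysis model". A second-order interaction needs a third factor, and the section does not name one. The other is the general rule for p-values below 0.05 and 0.10. It follows the text on interactions and is not tied to a site comparison. The stated response to an interaction concerns BV: "If there is unexpected significant or near-significant interaction, we will stratify on BV status".

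Section 11.7 enlarges the sample for a "5% Inner Class Correlation (ICC) for correlation of the subjects within the 4 sites". Sections 5.1, 11.9 and 12 name three clinical sites, while sections 11.2, 11.7 and 14.4 refer to four.

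**The concern.** When randomization is stratified, the usual practice is to carry the stratum into the analysis and to say so in advance. Here a check of unstated content decides it. Two analysts following 11.13 faithfully could report different primary models, one that nearly always contains site and one that rarely does. The trial is unblinded and is analysed by the lead institution's own staff, so a choice left open until data are in hand is better closed.

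The interaction (H2) is more exposed than the overall arm comparison (H1). Blocking balances the arms within each site, but it does not balance BV within site.

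**Working it through.** **The plan's own figures.** With p1 = 0.162, p2 = 0.107, mean 0.1345, two-sided 5% and power 0.80:

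n per arm = [1.960 × √(2 × 0.1345 × 0.8655) + 0.842 × √(0.162 × 0.838 + 0.107 × 0.893)]² / 0.055² = 603, so 1206 in total, as in 11.7.

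The 15% equals (4 − 1) × 0.05. Then 1206 × 1.15 × 1.20 = 1664, and 1664 × 0.80 = 1331 (the plan says 1332). Fixing site in the model changes none of these.

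**Inputs for the effect of site.**
- From 11.7: 1332 evaluable women and rates of 16.2% and 10.7%.
- From 2.2: BV in 61%, the share seen in HIV-positive women with TV.
- Assumed: three equal sites (222 women per arm per site), BV as a baseline factor equally common in both arms and at every site, two-sided 5% Wald tests, and the site rates below. The documents give no rates by site.
- Effect placed only in women with BV, as H2 states. Their single-dose rate is (0.162 − 0.39 × 0.107)/0.61 = 19.7%, and every other cell is 10.7%.

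**Site rates.** On the proportion scale, ICC = between-site variance / [p(1 − p)].
- Single-dose rates of 7.2/14.5/26.9%: (9.0² + 1.7² + 10.7²)/3 = 66.1 in squared percentage points, and 0.00661/(0.162 × 0.838) = 0.049, about 5%.
- Rates of 11.9/15.9/20.8%: (4.3² + 0.3² + 4.6²)/3 = 13.2, and 0.00132/0.1358 = 0.010, or 1%.
- On the logit scale, 5% gives a site variance of 0.05 × (π²/3)/0.95 = 0.173, SD 0.416.

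**H2 results.** Power comes from 200,000 simulated trials per setting. Ranges are across repeated runs. "Rate check" means that site is added when a chi-square test of site TV-positive rates gives p < 0.05.

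| Site variation | H2 power, site out / in | Verdicts differ, never v always | Verdicts differ, rate check v always |
|---|---|---|---|
| None | 53.9 / 53.9% | 0.9–1.0% | 0.8–0.9% |
| ICC 1% | 53.8 / 54.3% | 2.8–2.9% | 0.2–0.3% |
| ICC 5%, logit scale | 53.8 / 54.4% | 3.1% | not run; cannot exceed 3.1% |
| ICC 5%, proportion scale | 54.0 / 56.3% | 6.2–6.4% | 0.0% |

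The plan's rule can disagree with always including site only in trials where site is left out. The never-v-always column is therefore an upper limit for any reading of the rule.

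- **Read as a site-rate check**, site enters in 86% of trials at ICC 1%, 72% at logit-scale 5% and 100% at proportion-scale 5%. It is present when it matters.
- **Read as a check of arm-effect heterogeneity**, site enters in only about 5% of trials (p < 0.05) or 10% (p < 0.10) in each setting. Disagreement is then close to the upper limit. If the trigger is unrelated to which trials disagree, it is about 0.95 × 6.4 = 6.1% at proportion-scale 5% and 0.95 × 2.9 = 2.8% at ICC 1%.

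At proportion-scale 5%, the never-v-always figure is 6.3% with BV in 67% (155/230, Table 4), 1.7% with BV in 29% (the national figure in 2.2), and 6.7% with four sites.

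**H1** (arm comparison without BV terms), power with site out / in: 83.8/83.8% (none), 83.9/84.2% (ICC 1%), 83.3/83.7% (logit-scale 5%), 84.5/85.5% (proportion-scale 5%). Verdicts differ in at most 1.1%.

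**Type I error.** For H2 it is 4.9–5.0% with site out or in, and 4.7–5.0% under the rate check. For H1 at proportion-scale 5% it is 4.4% with site out and 5.0% with site in, so omission is slightly conservative.

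**The case against.** The strongest reply is that the plan does not omit site. It adds site when sites differ. If the check is on TV-positive rates, the rule gives almost the same H2 verdicts as a fixed site term. That is right, and it limits the size of this point. What remains is that the plan never says this is the check.

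The fourfold spread in site rates behind the 6% figure is also hard to square with the similar study populations that 11.13 expects. Nor does 11.7 establish a true ICC of 5%, because its 15% uses the number of sites as M. With women per site instead (1332/4 = 333), 15% corresponds to an ICC of 0.15/332, or about 0.0005. The 6% is an upper case, not an expectation.

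Three stronger readings are tempting, and the documents do not support them:
- **That 11.7 and 11.13 contradict each other on site.** Allowing for possible clustering in the sample size, not expecting it and then checking is ordinary caution.
- **That leaving site out inflates false positives.** It does not. If someone could choose the more favourable model, H2 type I error would be at most about 5.9%, but 11.13 ties inclusion to site differences, not to the treatment result.
- **That fixing site fully fixes the model.** Section 11.13 also says of imbalanced factors that "associations will be explored for potential confounding and if found these factors will also be included in the model", and it stratifies on BV at p < 0.10. Those are separate issues.

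A last objection is that adding site changes the odds ratio. At proportion-scale 5%, the log odds ratio in women with BV moves from −0.722 (SE 0.205) to −0.758 (SE 0.210). This is the expected shift from a marginal to a conditional estimate, not bias. Model (1) already conditions on BV, and the plan already permits site in it.

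**Conclusion.** The point holds as one of prespecification. Whether the randomization stratum is in the primary model is settled after data are seen, by a check whose subject is not stated. It is worth correcting, but it does not threaten the trial's conclusions. Type I error stays near 5%, and H1 power moves by about 1 point or less. H2 verdicts change in under 1% of trials if the check is on site TV-positive rates. They change in up to about 6% only under the heterogeneity reading with roughly fourfold site differences, and in about 3% or less at an ICC of 1%.

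These figures rest on assumed site rates, three equal sites, and BV as a baseline factor equally common in both arms. Section 11.13 describes the BV term as status at the visit without saying which visit. If follow-up BV is meant, the arms could differ in BV and the H2 figures would not apply as they stand. The lack of prespecification does not depend on any of these assumptions.

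**What to change.** In 11.13, define model (1) as arm + BV + arm-by-BV + site, with site a fixed factor whatever differences are observed, and delete the condition. Report site-by-arm heterogeneity as a descriptive check that changes no model. Set the site levels to the sites that actually randomize, after reconciling three with four across sections 5.1, 11.2, 11.7, 11.9, 12 and 14.4.

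The cost is one changed sentence and two extra parameters (three with four sites). Expected TV-positive results number between about 120 (the genotyping estimate in 7.2.2.2) and 666 × 0.162 + 666 × 0.107 = 179. With three sites and 120 events, six coefficients leave 120/6 = 20 events each. The reported odds ratio becomes conditional on site as well as BV, which the plan should state. The sample size stands.

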Study Duration	Participants will be enrolled in the study for the time it takes to complete their follow up visits (no more than 21 weeks). Accrual for the study will be 30 months in duration. Participants will be asked for permission to store their samples for future research and for investigators to use their data for secondary data analyses.
Study Agent/Intervention Description	Metronidazole 2g single oral dose under direct observation and Metronidazole 500 mg oral dose BID for 7 days with the first dose given under direct observation
Primary Objective	To examine the influence of two factors on repeat infections with TV among HIV negative women: dosing and the presence of bacterial vaginosis (BV):  We will test two hypotheses: H1: Women receiving multi-day MTZ will be less likely to test TV positive at TOC compared to women who receive the single dose MTZ.  H2: This effect (H1) will only be observed among women who have BV (Nugent score $\geq 7$ ).
Secondary Objectives	To determine the proportion of infections at follow up that are attributable to treatment failure or sexual re-exposure.
Exploratory Objectives	Examination of the rate and factors associated with adherence to medication, knowledge/belief/factors associated with partner treatment, sexual exposure and the nature of the sexual act and sexual partner, and condom use will be possible using the ACASI survey data. These factors will be assessed by arm to determine if any confounding occurred and if so, these analyses will be adjusted for these factors. These data will also help inform future translational research.
Endpoints	Repeat infection with Trichomonas vaginalis (TV) at 4 weeks (TOC) as measured by InPouch culture or NAAT.

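### H1 and H2 are both primary and each is judged at 0.05 with no testing order, so the two-sided chance of a false primary claim is about 7% to 10% rather than 5%

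*Combined protocol and SAP*

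**What the plan says.** The Protocol Summary lists H1 and H2 together under the primary objective ("We will test two hypotheses"). Section 3.1 numbers both as primary, and Section 4.2.1 gives one primary endpoint for both aims. Section 11.7 adds: "This study examines two hypotheses simultaneously".

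Section 11.13 answers both from one logistic model, model (1): "This primary logistic model contains two main effects (i.e. treatment and BV"), plus their interaction. The significance rule is "We will consider any p-value less than 0.05 to be significant and any p-value less than 0.10 as near-significant". Shortly before it, the plan states: "We do not anticipate a three-way interaction, and our simulations (see below) support that belief". The sentence after the rule begins: "If there is unexpected significant or near-significant interaction, we will stratify on BV status".

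The only order given is of models: a fully parameterised model is run before model (1). Section 11.3 describes BV-stratified comparisons as additional analyses. Section 11.12 sees no need for efficacy interim analyses.

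**The concern.** Two primary tests at the full 0.05, with success open to either, give more than a 5% chance that at least one is falsely positive. H2 is defined through H1, since it says where the H1 effect is found, yet no rule makes its test wait for H1. Followed as written, the plan allows a primary claim to rest on a subgroup interaction while the overall comparison fails. Sections 2.1 and 4.1 expect the results to inform treatment guidelines rapidly, so the status of such a claim matters.

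The plan also does not say which contrast tests H1. Model (1) contains the interaction. With 0/1 coding, its treatment coefficient is the effect in BV-negative women only, which is not the overall comparison that H1 describes.

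**Working it through.** **1. The plan's own figure.** Section 11.7 gives "16.2% for single dose and 10.7% for multi dose at a power of 0.80, we will need 1206 subjects", with no alpha or sidedness. Using the two-proportion formula with pooled null variance, two-sided 0.05 and mean rate 0.1345:

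n per arm = [1.960 × √(2 × 0.1345 × 0.8655) + 0.842 × √(0.162 × 0.838 + 0.107 × 0.893)]² / 0.055² = 602.9, so 603 per arm and **1206** in total.

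The other variants tried do not match: one-sided gives 950, and two-sided with continuity correction gives 1278. Then 1206 × 1.15 × 1.20 = 1664.3, the stated 1664. The design therefore matches one two-sided 0.05 test of H1.

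**2. Inputs for the error rate.** There are 1332 evaluable women (Section 11.7), or 666 per arm. BV prevalence in this population is not stated. It was 61% in the HIV-positive screening study (Section 2.2), and Table 4 gives 155/230 = 67%. I assume a range of 30% to 67%; prevalence affects only the correlation between the tests. All rates below are two-sided, with no treatment effect and no interaction.

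**3. H1 as the pooled effect, H2 as the interaction, each at 0.05.** Let b₊ and b₋ be the log odds ratios in the BV-positive and BV-negative strata, with variances v₊ and v₋. The inverse-variance pooled estimate is uncorrelated with b₊ − b₋, because each weight times its variance gives the same constant and the two terms cancel. The tests are then asymptotically independent:

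1 − 0.95² = **9.75%**.

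Normal simulation gives 9.7% to 9.8%. Binomial simulation at 666 per arm gives 9.1% to 9.4%.

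**4. H1 as the model (1) treatment coefficient, 0/1 coding.** This tests b₋. Its correlation with the interaction statistic is −√f, where f is BV prevalence (about −0.55 at 30%, −0.82 at 67%). The overlap lowers the union to 8.9% at f = 30% and 7.6% at f = 67%. Binomial checks run from about 8.6% down to 7.2%.

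**5. Adding the 0.10 trigger.** Suppose the trigger covers the treatment-by-BV interaction, so that interaction p below 0.10 opens stratum tests at 0.05. Count a claim from the H1 test, the interaction at 0.05, or an opened stratum test.

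| H1 contrast | Two tests at 0.05 | With 0.10 trigger opening strata |
|---|---|---|
| Pooled effect | 9.1% to 9.8% | 10.6% to 11.2% |
| Model (1) coefficient, 0/1 coding | 7.2% to 8.9% | 8.0% to 9.9% |

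**6. Counting interaction p below 0.10 as a claim in itself.** 1 − 0.95 × 0.90 = 14.5% (binomial about 14%).

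**7. Remedies.** In a fixed sequence, nothing can be claimed unless H1 is rejected, so the error with no effect is the 5% of the H1 test. If H1 is true and there is no interaction, the only possible false claim is the interaction, itself at 5%. The sample size stays at 1206 and 1664. With Bonferroni at 0.025 each, the error is 1 − 0.975² = 4.94%, but H1 needs 1462 evaluable women, and 1462 × 1.15 × 1.20 gives about 2018 enrolled. With 1332 evaluable and no design-effect deflation, H1 power would fall from 83.8% to 75.9%.

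**The case against.** **The 0.10 rule is not a claim threshold.** A reader might infer that H2 can be declared at 0.10, a looser standard for the subgroup claim, and so an error of 14%. The documents do not support this. Only p below 0.05 is called significant, and the stated consequence of near-significance is stratification.

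**The rule may not concern H2 at all.** It follows the discussion of a three-way interaction and speaks of an unexpected one, whereas the treatment-by-BV term is what H2 predicts. It also calls for examining any remaining interaction within each BV group, where no treatment-by-BV interaction can exist. That favours the reading that the rule concerns another term. Against that, model (1) has only two factors, no third is named, and the prescribed action is to split by BV. The scope is unclear, so the 11% figure is conditional.

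**Both hypotheses are directional.** Counting only results in the hypothesised direction gives about 4.9% (1 − 0.975² = 4.94%). That is correct, but the matching rate for a single test is 2.5%, so the error still roughly doubles.

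**Stratified rates are already planned.** Section 11.3 provides for them without any trigger. That stands; what it lacks is a commitment to confidence intervals. Calling those comparisons additional also sits awkwardly with H2 being primary.

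**Conclusion.** The point holds. Two primary hypotheses, each judged at 0.05 with no order or split, give a two-sided chance of about 7% to 10% of at least one false primary claim. The upper end applies if H1 is the pooled effect, the lower end if it is the 0/1-coded model (1) coefficient. It rises to about 11% only if H1 is the pooled effect and the 0.10 trigger also covers the treatment-by-BV interaction. The 14% figure is not the plan's rule.

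These rates assume no effect in either BV group, 1:1 allocation, 666 evaluable per arm, no site clustering, no interim efficacy testing and BV prevalence between 30% and 67%. They also treat BV as fixed at baseline; model (1) labels it as measured at the visit without saying which one. This is more than a missing detail, because following the stated rule exactly produces the excess error.

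**What to change.** In Section 11.13:

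- Test H1 first, as the overall treatment effect at two-sided 0.05, and name that contrast. Do not use the treatment coefficient of model (1).
- Test H2 by the treatment-by-BV interaction at two-sided 0.05, only if H1 is significant.
- State that p below 0.10 supports no primary claim, and that the rule for an unexpected interaction does not govern the H2 term.
- Report the arm difference with a 95% confidence interval in each BV stratum, whatever the interaction p-value. A significant interaction shows that the effects differ; it does not show that the effect occurs only in women with BV.

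This changes wording only. H1 keeps its full 0.05 and its power, and enrolment stays at 1664. The cost is that H2 cannot be claimed as confirmatory if H1 is not significant, a limited loss because H2 is defined through H1.
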